Appendix 2 Reference for Fatty Acid Profile Values (Mayo Clinic References)

Fatty Acid	Chain Length	Reference Values
Stearic Acid	C18:0	<1 year: 270-1,140 nmol/mL
		1-17 years: 280-1,170 nmol/mL
		> or =18 years: 590-1,170 nmol/mL
Eicosapentaenoic Acid (EPA)	C20:5n-3	<1 year: 2-60 nmol/mL
		1-17 years: 8-90 nmol/mL
		> or =18 years: 14-100 nmol/mL
Arachidonic Acid (ARA)	C20:4n-6	<1 year: 110-1,110 nmol/mL
		1-17 years: 350-1,030 nmol/mL
		> or =18 years: 520-1,490 nmol/mL
Eicosatrienoic Acid (Mead acid)	C20:3n-9	1-31 days: 8-60 nmol/mL
		32 days-11 months: 3-24 nmol/mL
		1-17 years: 7-30 nmol/mL
		> or =18 years: 7-30 nmol/mL
Homo-Gamma-Linolenic	C20:3n-6	<1 year: 30-170 nmol/mL
		1-17 years: 60-220 nmol/mL
		> or =18 years: 50-250 nmol/mL
Arachidic Acid	C20:0	<1 year: 30-120 nmol/mL
		1-17 years: 30-90 nmol/mL
		> or =18 years: 50-90 nmol/mL
Docosahexaenoic Acid (DHA)	C22:6n-3	<1 year: 10-220 nmol/mL
		1-17 years: 30-160 nmol/mL
		> or =18 years: 30-250 nmol/mL
DPA	C22:5n-6	<1 year: 3-70 nmol/mL
		1-17 years: 10-50 nmol/mL
		> or =18 years: 10-70 nmol/mL
DPA	C22:5n-3	<1 year: 6-110 nmol/mL
		1-17 years: 30-270 nmol/mL
		> or =18 years: 20-210 nmol/mL
DTA	C22:4n-6	<1 year: 2-50 nmol/mL
		1-17 years: 10-40 nmol/mL
		> or =18 years: 10-80 nmol/mL
Docosenoic Acid	C22:1	<1 year: 2-20 nmol/mL
		1-17 years: 4-13 nmol/mL

Fatty Acid	Chain Length	Reference Values
		> or =18 years: 4-13 nmol/mL
Nervonic Acid	C24:1n-9	<1 year: 30-150 nmol/mL
		1-17 years: 50-130 nmol/mL
		> or =18 years: 60-100 nmol/mL
Total Saturated Acid	N/A	<1 year: 1.2-4.6 mmol/L
		1-17 years: 1.4-4.9 mmol/L
		> or =18 years: 2.5-5.5 mmol/L
Total Monounsaturated Acid	N/A	<1 year: 0.3-4.6 mmol/L
		1-17 years: 0.5-4.4 mmol/L
		> or =18 years: 1.3-5.8 mmol/L
Total Polyunsaturated Acid	N/A	<1 year: 1.1-4.9 mmol/L
		1-17 years: 1.7-5.3 mmol/L
		> or =18 years: 3.2-5.8 mmol/L
Total n-3 Fatty Acids	N/A	<1 year: 0.0-0.4 mmol/L
		1-17 years: 0.1-0.5 mmol/L
		> or =18 years: 0.2-0.5 mmol/L
Total n-6 Fatty Acids	N/A	<1 year: 0.9-4.4 mmol/L
		1-17 years: 1.6-4.7 mmol/L
		> or =18 years: 3.0-5.4 mmol/L
Total Fatty Acids	N/A	<1 year: 3.3-14.0 mmol/L
		1-17 years: 4.4-14.3 mmol/L
		> or =18 years: 7.3-16.8 mmol/L

Statistical Analysis Plan: 6344-001

Study Number:6344-001Study Phase:IVStudy DesignThis is a multi-center, randomized, double-blind, controlled, 2-arm, prospective study to evaluate occurrence of essential fatty acid deficiency (EFAD) (diagnosed by Holman Index >0.4) in 100 randomized pediatric patients including neonates, to either Clinolipid or standard-of-care soybean oil- based Intralipid. The study will be conducted at approximately 10 sites in the US.Product Name:Clinolipid (lipid injectable emulsion, USP) 20%Indication:Clinolipid 20% is a lipid emulsion currently indicated for parenteral nutrition in adults providing a source of calories and essential fatty acids when oral or enteral nutrition is not possible, insufficient, or contraindicatedStatistician:Baxter Healthcare Corporation [name] Deerfield, Illinois 60015, USAResponsible Medical Officer:MD, FACP	Study Number:6344-001Study Phase:IVStudy DesignThis is a multi-center, randomized, double-blind, controlled, 2-arm, prospective study to evaluate occurrence of essential fatty acid deficiency (EFAD) (diagnosed by Holman Index >0.4) in 100 randomized pediatric patients including neonates, to either Clinolipid or standard-of-care soybean oil- based Intralipid. The study will be conducted at approximately 10 sites in the US.Product Name:Clinolipid (lipid injectable emulsion, USP) 20%Indication:Clinolipid 20% is a lipid emulsion currently indicated for parenteral nutrition in adults providing a source of calories and essential fatty acids when oral or enteral nutrition is not possible, insufficient, or contraindicatedSponsor:Baxter Healthcare Corporation [name] Deerfield, Illinois 60015, USAResponsible Medical Officer:Image: Supproximate	Study Number: 6344-001 Study Phase: IV Study Design This is a multi-center, randomized, double-blind, controlled, 2-arm, prospective study to evaluate occurrence of essential fatty acid deficiency (EFAD) (diagnosed by Holman Index >0.4) in 100 randomized pediatric patients including neonates, to either Clinolipid or standard-of-care soybean oilbased Intralipid. The study will be conducted at approximately 10 sites in the US. Product Name: Clinolipid (lipid injectable emulsion, USP) 20% Indication: Clinolipid 20% is a lipid emulsion currently indicated for parenteral nutrition in adults providing a source of calories and essential fatty acids when oral or enteral nutrition is not possible, insufficient, or contraindicated Statistician: Sponsor: Baxter Healthcare Corporation [name] Responsible Medical Officer: MD, FACP Final Date: 30JAN2023	Study Title:	A Randomized, Double-Blind, Controlled, Clinical Trial to Evaluate the Risk of Developing Essential Fatty Acid Deficiency in Pediatric Patients, Including Neonates, Receiving Either Clinolipid (lipid injectable emulsion, USP) 20% or Standard- of-Care Soybean Oil-Based Lipid Emulsion
Study Phase:IVStudy DesignThis is a multi-center, randomized, double-blind, controlled, 2-arm, prospective study to evaluate occurrence of essential fatty acid deficiency (EFAD) (diagnosed by Holman Index >0.4) in 100 randomized pediatric patients including neonates, to either Clinolipid or standard-of-care soybean oil- based Intralipid. The study will be conducted at approximately 10 sites in the US.Product Name:Clinolipid (lipid injectable emulsion, USP) 20%Indication:Clinolipid 20% is a lipid emulsion currently indicated for parenteral nutrition in adults providing a source of calories and essential fatty acids when oral or enteral nutrition is not possible, insufficient, or contraindicatedStatistician:Baxter Healthcare Corporation [name] Deerfield, Illinois 60015, USAResponsible Medical Officer:Heateret	Study Phase:IVStudy DesignThis is a multi-center, randomized, double-blind, controlled, 2-arm, prospective study to evaluate occurrence of essential fatty acid deficiency (EFAD) (diagnosed by Holman Index >0.4) in 100 randomized pediatric patients including neonates, to either Clinolipid or standard-of-care soybean oil- based Intralipid. The study will be conducted at approximately 10 sites in the US.Product Name:Clinolipid (lipid injectable emulsion, USP) 20%Indication:Clinolipid 20% is a lipid emulsion currently indicated for parenteral nutrition in adults providing a source of calories and essential fatty acids when oral or enteral nutrition is not possible, insufficient, or contraindicatedStatistician:Saster Healthcare Corporation [name] Deerfield, Illinois 60015, USAResponsible Medical Officer:MD, FACPFinal Date:30JAN2023	Study Phase:IVStudy DesignThis is a multi-center, randomized, double-blind, controlled, 2-arm, prospective study to evaluate occurrence of essential fatty acid deficiency (EFAD) (diagnosed by Holman Index >0.4) in 100 randomized pediatric patients including neonates, to either Clinolipid or standard-of-care soybean oil- based Intralipid. The study will be conducted at approximately 10 sites in the US.Product Name:Clinolipid (lipid injectable emulsion, USP) 20%Indication:Clinolipid 20% is a lipid emulsion currently indicated for parenteral nutrition in adults providing a source of calories and essential fatty acids when oral or enteral nutrition is not possible, insufficient, or contraindicatedStatistician:Sector Parkway Deerfield, Illinois 60015, USAResponsible Medical Officer:Mon. FACPFinal Date:30JAN2023	Study Number:	6344-001
Study DesignThis is a multi-center, randomized, double-blind, controlled, 2-arm, prospective study to evaluate occurrence of essential fatty acid deficiency (EFAD) (diagnosed by Holman Index >0.4) in 100 randomized pediatric patients including neonates, to either Clinolipid or standard-of-care soybean oil- based Intralipid. The study will be conducted at approximately 10 sites in the US.Product Name:Clinolipid (lipid injectable emulsion, USP) 20%Indication:Clinolipid 20% is a lipid emulsion currently indicated for parenteral nutrition in adults providing a source of calories and essential fatty acids when oral or enteral nutrition is not possible, insufficient, or contraindicatedStatistician:Saster Healthcare Corporation [name] Deerfield, Illinois 60015, USAResponsible Medical Officer:MD, FACP	Study DesignThis is a multi-center, randomized, double-blind, controlled, 2-arm, prospective study to evaluate occurrence of essential fatty acid deficiency (EFAD) (diagnosed by Holman Index >0.4) in 100 randomized pediatric patients including neonates, to either Clinolipid or standard-of-care soybean oil- based Intralipid. The study will be conducted at approximately 10 sites in the US.Product Name:Clinolipid (lipid injectable emulsion, USP) 20%Indication:Clinolipid 20% is a lipid emulsion currently indicated for parenteral nutrition in adults providing a source of calories and essential fatty acids when oral or enteral nutrition is not possible, insufficient, or contraindicatedStatistician:Saster Healthcare Corporation [name] Deerfield, Illinois 60015, USAResponsible Medical Officer:MD, FACPFinal Date:30JAN2023	Study DesignThis is a multi-center, randomized, double-blind, controlled, 2-arm, prospective study to evaluate occurrence of essential fatty acid deficiency (EFAD) (diagnosed by Holman Index >0.4) in 100 randomized pediatric patients including neonates, to either Clinolipid or standard-of-care soybean oil- based Intralipid. The study will be conducted at approximately 10 sites in the US.Product Name:Clinolipid (lipid injectable emulsion, USP) 20%Indication:Clinolipid 20% is a lipid emulsion currently indicated for parenteral nutrition in adults providing a source of calories and essential fatty acids when oral or enteral nutrition is not possible, insufficient, or contraindicatedSponsor:Baxter Healthcare Corporation [name] Deerfield, Illinois 60015, USAResponsible Medical Officer:MD, FACPFinal Date:30JAN2023	Study Phase:	IV
Product Name:Clinolipid (lipid injectable emulsion, USP) 20%Indication:Clinolipid 20% is a lipid emulsion currently indicated for parenteral nutrition in adults providing a source of calories and essential fatty acids when oral or enteral nutrition is not possible, insufficient, or contraindicatedStatistician:EmployeeSponsor:Baxter Healthcare Corporation [name] Deerfield, Illinois 60015, USAResponsible Medical Officer:Employee	Product Name:Clinolipid (lipid injectable emulsion, USP) 20%Indication:Clinolipid 20% is a lipid emulsion currently indicated for parenteral nutrition in adults providing a source of calories and essential fatty acids when oral or enteral nutrition is not possible, insufficient, or contraindicatedStatistician:Satter Healthcare Corporation [name] Deerfield, Illinois 60015, USAResponsible Medical Officer:Source of calories and essential fatty acids when oral or enteral nutrition is not possible, insufficient, or contraindicatedFinal Date:30JAN2023	Product Name:Clinolipid (lipid injectable emulsion, USP) 20%Indication:Clinolipid 20% is a lipid emulsion currently indicated for parenteral nutrition in adults providing a source of calories and essential fatty acids when oral or enteral nutrition is not possible, insufficient, or contraindicatedStatistician:Saster Healthcare Corporation [name] Deerfield, Illinois 60015, USAResponsible Medical Officer:MD, FACPFinal Date:30JAN2023	Study Design	This is a multi-center, randomized, double-blind, controlled, 2-arm, prospective study to evaluate occurrence of essential fatty acid deficiency (EFAD) (diagnosed by Holman Index >0.4) in 100 randomized pediatric patients including neonates, to either Clinolipid or standard-of-care soybean oil- based Intralipid. The study will be conducted at approximately 10 sites in the US.

DSMB	Data Safety and Monitoring Board
eCRF	Electronic Case Report Form
EFAD	Essential Fatty Acid Deficiency
EPA	Eicosapentaenoic Acid
FA	Fatty Acid
FADS1	Fatty Acid Desaturase 1 Gene
FADS2	Fatty Acid Desaturase 2 Gene
FAS	Full Analysis Set
GA	Gestational Age
GGT	Gamma-Glutamyl Transferase
hCG	Human Chorionic Gonadotropin
Hct	Hematocrit
Hgb	Hemoglobin
ICF	Informed Consent Form
ILE	Intravenous Lipid Emulsion
IVH	Intraventricular Hemorrhage
IWRS	Interactive Web Response System
Κ	Potassium
LA	Linoleic acid

—

Pa	ge 7	of	46
30	JAN	J20	23

MCH	Mean Corpuscular Hemoglobin
MCHC	MCH Concentration
MedDRA	Medical Dictionary for Regulatory Activities
Mg	Magnesium
MPV	Mean Platelet Volume
Na	Sodium
NEC	Necrotizing Enterocolitis
Р	Phosphorus
PN	Parenteral Nutrition
PNALD	Parenteral Nutrition-Associated Liver Disease
PPS	Per Protocol Set
РТ	Preferred Term
PVL	Periventricular Leukomalacia
Q1	First Quartile
Q3	Third Quartile
RBC	Red Blood Cells
ROP	Retinopathy of Prematurity
SAE	Serious Adverse Event
SAP	Statistical Analysis Plan
SD	Standard Deviation
SDS	Standard Deviation Score
SDTM	Study Data Tabulation Models
SNPs	Single Nucleotide Polymorphisms
SOC	System Organ Class
SS	Safety Set
TB	Total Bilirubin
TEAE	Treatment Emergent Adverse Event
TLFs	Tables, Listings, and Figures
ULN	Upper Limit of Normal
USPI	United States Prescribing Information
WBC	White Blood Cells
WHO	World Health Organization

1. STUDY DETAILS

This statistical analysis plan (SAP) is provided to describe the framework for the reporting, summarization, and statistical analysis methodology of the safety and efficacy parameters measured throughout the study. It is based on clinical trial protocol 6344-001 amendment version 5.6, dated 22 Feb 2022.

1.3 Secondary Objective(s)

The secondary objectives in patients receiving either Clinolipid or Intralipid are to evaluate:

- The risk of developing liver disease including parenteral nutrition-associated liver disease (PNALD):
 - PNALD will be defined by direct bilirubin ≥2 mg/dL when no other etiology for liver dysfunction is present;
 - Hepatic integrity will be assessed by measuring plasma liver function tests: alkaline phosphatase (ALP), aspartate aminotransferase (AST), alanine aminotransferase (ALT), gamma-glutamyl transferase (GGT), and total and direct bilirubin;
 - Plasma main phytosterols (stigmasterol, campesterol, sitosterol), cholesterol and squalene levels will be assessed. Phytosterols levels will be correlated with the risk of developing PNALD.
- The adequacy of nutritional interventions:
 - Prescribed and actual nutritional intakes (energy, protein, carbohydrates, and lipid) from both PN and enteral/oral nutrition will be collected and recorded on a daily basis and summarized on a daily basis during the first 2 weeks of treatment and on an approximately 15-day basis afterwards up to the end of study treatment in each of the treatment groups.
 - Growth will be assessed and evaluated from baseline to end of study treatment on an approximately every 15-day basis using descriptive summary statistics for weight, and height/length (and head circumference in infant <1 year) in each of the treatment groups as follows:
 - Gain in weight (g/kg/day in infants <1 year of age, g/day in children and adolescents) and gain in length/height (mm/week in all) and head circumference (mm/week in infants <1 year);
 - Changes in the standard deviation score (SDS or z-score) from reference growth curves (Fenton growth curve for premature infants, World Health Organization (WHO) growth standards for infants and children ages 0 to 2 years, or Center for Disease Control (CDC) growth charts for children age ≥2 years).
- The safety profiles of Clinolipid and Intralipid, as assessed by adverse events (AEs), serious adverse events (SAEs) and AEs of special interest (AESIs)
 - AESIs are known AEs related to PN with Intravenous Lipid Emulsions (ILEs), per Intralipid and Clinolipid United States Prescribing Information

(USPI) and include the following: catheter related infection, thrombophlebitis; EFAD as well as ILE-related Immediate or Early adverse reactions including: dyspnea, cyanosis, allergic reactions, hyperlipemia, hypercoagulability, nausea, vomiting, headache, flushing, increase in temperature, sweating, sleepiness, pain in the chest and back, slight pressure over the eyes, dizziness, irritation at the site of infusion, and ILE-related delayed adverse reactions including: hepatomegaly, jaundice, splenomegaly, thrombocytopenia, leukopenia, transient increases in liver function tests, and overloading syndrome (focal seizures, fever, leukocytosis, hepatomegaly, splenomegaly and shock).

1.4 Study Design

1.4.1 Overall Study Design and Plan

This is a multi-center, randomized, double-blind, controlled, safety and efficacy study to evaluate the occurrence of EFAD (diagnosed by Holman Index >0.4) in pediatric patients receiving either Clinolipid or standard-of-care soybean oil-based ILE (Intralipid) in the hospital setting from 7 up to 90 days as part of PN. The risk of developing liver disease, including PNALD (defined by direct bilirubin $\geq 2 \text{ mg/dL}$) when no other etiology for liver dysfunction is present, also will be assessed.

Approximately 100 pediatric patients, including neonates, will participate in the study. Patients will be randomized in a 1:1 ratio to the treatment groups (Clinolipid or Intralipid) according to a central dynamic randomization scheme stratified by site and age group (premature infants born <37 weeks of gestation, full-term neonates born \geq 37 weeks of gestation to <1 month of age, infants 1 to <12 months of age, children 1 to <10 years of age, adolescent 10 to <18 years of age). In the case of multiple birth pregnancies, the infants will be assigned to the same treatment group.

Holman Index and FA profile will be evaluated. Select polymorphisms in the FA desaturase genes FADS1 and FADS2, will be determined in a subset of patients. The major plasma phytosterols found in the ILEs (stigmasterol, campesterol, sitosterol), cholesterol, and squalene will also be assessed.

The study consists of a Screening Period to confirm the patient's eligibility for the study after the informed consent form (ICF) and assent (if applicable) is signed and a Treatment Period, where study Day 1 is defined as the first day the patient receives study treatment.

End of study treatment is defined as the last day of PN with Intralipid or Clinolipid; maximum 90 days of study treatment is allowed.

1.4.2 Determination of Sample Size

The sample size of 100 patients (50 in each of the 2 treatment groups: Clinolipid vs Intralipid), including neonates, is based on the feasibility of timely enrollment of patients for generating reference data and summary descriptive statistics, rather than on a formal power calculation. No formal hypothesis testing is planned.

1.4.3 Randomization Procedure

Approximately 100 pediatric patients, including neonates, will participate in the study. Patients will be randomized in a 1:1 ratio to the treatment groups (Clinolipid or Intralipid) according to a central dynamic randomization scheme stratified by site and age group (premature infants born <37 weeks of gestation, full-term neonates born ≥37 weeks of gestation to <1 month of age, infants 1 to <12 months of age, children 1 to <10 years of age, adolescent 10 to <18 years of age). In the case of multiple birth pregnancies, the infants will be assigned to the same treatment group.

For this study, a patient should be randomized within 24 hours of signing informed consent, when possible, but must be randomized within 3 days of signing informed consent. See randomization plan for more details.

1.4.4 Blinding

This is a double blinded study and most study roles will be blinded except the unblinded statistician, unblinded clinical project manager, clinical supplies manager and unblinded CRA. The pharmacist(s) involved in the study medication preparation will also be unblinded.

The dynamic randomization will be built using Prancer software and no end user will have direct access to the patient level randomization codes. The statistician that reviews the randomization scheme via simulations will not have any access to the patient level randomization codes and therefore will remain blinded.

Planned unblinding of the study will take place for the Data Safety and Monitoring Board (DSMB) meetings and all unblinding activities are outsourced to a secondary team at the Contract Research Organization (CRO). See DSMB Charter for more details.

Dry runs of SDTM/ADaM data and tables, listings, and figures (TLFs) will be conducted in a blinded manner.

Final study unblinding after the final database lock will be requested by Baxter and unblinding codes will be provided by the IWRS manager.

Data points or parameters that are potentially unblinding are not foreseen for this study. All protocol deviations related to drug preparation by the unblinded pharmacist will not be shared with the study team prior to study unblinding.

Evaluation	Screening Baseline D		Study Treatment Day (every 15 days ±2 days)						End of Study Treatment ^o
		a		15	30	45	60	75	(± 2 days)
Informed consent / assent (as applicable)	x								
Confirm eligibility	X								
Randomization ^b	X								
Demographics ^c	X								
Medical history including diagnosis for requiring PN	x	х							
Physical examination including length or height and head circumference	х	х		x	x	x	x	x	х
Body weight ^d	X	Х	X	X	X	X	X	X	Х
Vital signs ^e	X	Х	X	X	X	X	X	X	Х
Diagnosis of neonatal morbidities ^f									х
Laboratory Evaluations									
Hematology and serum chemistry	x	х	Standard-of-Care and every 15 days ±2 days						
Triglyceride levels	Х	Х	Stand	lard-o	of-Ca	re and	l every	y 15 c	lays ±2 days
Hepatic function tests	х	х	Stand	lard-o	of-Ca	re and	every	y 15 d	lays ±2 days

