Clinolipid is an ILE comprised of a mixture of 80% OO and 20% SO. It was formulated with a lower SO content than currently marketed emulsions in order to reduce LA levels, while still providing an adequate amount of EFAs to prevent and correct EFAD in adult and pediatric patients requiring PN.¹⁵ This OO-based ILE is rich in oleic acid, an n-9 monounsaturated FA, that is considered immune neutral with potentially fewer adverse consequences on immunity compared to pure SO ILEs.¹⁰

Clinolipid has approximately one third of the LA content of a 100% SO ILE (fatty acid levels are provided in Table 1 and sterol composition is provided in Table 2). This reduction in the EFA supply could be a concern in a pediatric population, especially premature infants, who have higher EFA requirements than adults. Clinolipid has marketing authorization in approximately 50 countries. The current evidences of more than 20 years of clinical use suggest that Clinolipid is safe and can prevent EFAD.^{15,16} However, the objective of this study is to evaluate the risk of developing EFAD when using 20% Clinolipid in pediatric patients requiring PN compared to the use of a 100%

SO ILE (Intralipid 20%) that is still the standard-of-care (SOC) in current United States hospital settings.

Fatty Acid(s)	Intralipid 20%	Clinolipid 20%
Total Saturated Fatty Acids	15.6 %	16.6 %
Myristic acid (14:0)	0.1	0.0
Palmitic acid (16:0)	11.0	13.0
Stearic acid (18:0)	3.9	3.3
Total monounsaturated fatty acids	22.8 %	63.4 %
Palmitoleic acid (16:1n-7)	0.1	0.9
Oleic acid (18:1n-9)	20.9	59.7
Vaccenic acid (18:1n-7)	1.3	1.7
Gondoic acid (20:1n-9)	0.2	0.2
Total polyunsaturated fatty acids	61.7 %	20.0 %
Linoleic acid (18:2n-6)	54.7	18.6
γ-linolenic acid (18:3n-6)	ND	ND
α -linolenic acid (18:3n-3)	6.7	1.7
Arachidonic acid (20:4n-6)	0.2	0.2
EPA (20:5n-3)	ND	ND
DHA (22:6n-3)	0.1	0.1

Table 1. Fatty Acid Levels (mean levels) for Intralipid and Clinolipid

DHA = docosahexaenoic acid; EPA = eicosapentaenoic acid; ND = not detected; values represent mean % and are rounded to nearest tenth

Adapted from Harvey K et al.¹⁷

Sterols	Intralipid (Soybean Oil-Based)	Clinolipid (Olive Oil-based)
Squalene	7.43 ± 0.10	387.45 ± 2.30
Cholesterol	274.08 ± 3.55	109.70 ± 0.38
Campesterol	55.35 ± 0.48	13.33 ± 0.12
Stigmasterol	65.05 ± 0.52	12.15 ± 0.04
β-Sitosterol	302.64 ± 2.00	240.59 ± 2.08
β-Sitostanol	7.68 ± 0.25	4.57 ± 0.16
Lanosterol	8.35 ± 2.48	3.74 ± 0.20
Total sterols	713.15 ± 9.27	384.08 ± 2.98

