6.8.5 Calculating Linoleic Acid (LA) Intake from Intravenous Lipid Emulsion (ILE)

Clinolipid contains approximately 18.6% LA while Intralipid contains approximately 54.7% LA. Since both are 20% ILE (20 g/dL, 0.2 g/mL, 2 kcal/ml), the content of LA is approximately 0.11 g/mL for Intralipid (1.1 kcal/ml from LA) and 0.04 g/mL for Clinolipid (0.4 kcal/ml from LA) (Table 6).

Content	20% Intralipid	20% Clinolipid
Lipid, g/ml	0.2	0.2
Energy, kcal/ml	2	2
Linoleic acid, g/ml	0.11	0.04
Linoleic acid, kcal/ml	1.1	0.4

Table 6. Intralipid and Clinolipid Linoleic Acid Content

Sample Calculation:

If a 2 kg patient receives 16 mL of Intralipid per day, the patient receives 8 ml/kg/day of Intralipid. It corresponds to 1.6 g/kg/day of lipid and 0.88 g/kg/day of LA. The energy part of LA is 8.8 kcal/kg/day. If the total energy intake is 100 kcal/kg/day, it means that 8.8% of the energy intake comes from LA.

If a 2 kg patient receives 16 mL of Clinolipid per day, the patient receives 8 ml/kg/day of Clinolipid. It corresponds to 1.6 g/kg/day of lipid and 0.32 g/kg/day of LA. The energy part of LA is 3.2 kcal/kg/day. If the total energy intake is 100 kcal/kg/day, it means that 3.2% of the energy intake comes from LA.

The LA intake that normally prevents EFAD is 1-4% of total energy intake. The unblinded pharmacist determines if the patient has adequate LA intake for prevention of EFAD. The pharmacist communicates to the patient's nutrition clinician according to the protocol (see Sections 6.8.2, 6.8.3 and 6.8.4.).

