2.5.1 Adverse Events

2.5.1.1 Derivation of Adverse Events

Adverse events (AEs) will be coded using MedDRA. They will be classified as follows:

Pre-treatment adverse event – An adverse event that starts between the date of signing the informed consent form (ICF) and the study treatment

Treatment-emergent adverse event (TEAE) – An adverse event that starts on or after the start of study treatment

Treatment-emergent adverse events of special interest (AESI) - The following are called out as AESIs in the protocol: catheter related infection, thrombophlebitis, dyspnea, cyanosis, allergic reactions, hyperlipemia, hypercoagulability, nausea, vomiting, headache, flushing, increase in temperature, sweating, sleepiness, pain in the chest and back, slight pressure over the eyes, dizziness, irritation at the site of infusion, hepatomegaly, splenomegaly, thrombocytopenia, leukopenia, and overloading syndrome (focal seizures, fever, leukocytosis, hepatomegaly, splenomegaly and shock). A blinded review of AEs will be conducted at the end of the study before unblinding to flag AESIs.

An adverse event will be considered related to study treatment if they respond 'Probably related' or 'Possibly related' to relationship to study treatment.

In case of incomplete information on study treatment or AE onset, events will be classified as treatment-emergent unless there is sufficient data to rule out the possibility that the event started after the start of study treatment.

If the severity of an adverse event is missing, then that adverse event will be classified as *severe*. If relationship of an adverse event is missing, then that adverse event will be classified as *probably related*.

The number of events per 100 patient days will be calculated as follows:

$$\frac{\text{Number of Total Events}}{\sum_{i=1}^{n} (\text{End Date of Treatment}_{i} - \text{Start Date of Treatment}_{i} + 1)}, \\100$$

where i represents each patient and n represents the total number of patients in the Safety Set for that treatment group.

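### SAP 1.4.4 says no potentially unblinding data are foreseen, but the protocol's own composition tables and linoleic-acid arithmetic make such data foreseeable

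*SAP*

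**What the plan says.** SAP 1.4.4 (Blinding) states: "Data points or parameters that are potentially unblinding are not foreseen for this study". The only data it holds back from the study team are deviations in drug preparation by the unblinded pharmacist. It also says: "Dry runs of SDTM/ADaM data and tables, listings, and figures (TLFs) will be conducted in a blinded manner". It sets no masking rule for any laboratory result. SAP 2.5.1.1 then relies on the blind for a judged step: "A blinded review of AEs will be conducted at the end of the study before unblinding to flag AESIs".

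Protocol 5.5 keeps the assignment from investigators, site staff, central laboratory staff and the sponsor's data management, statistical and medical functions, apart from one unblinded sponsor statistician. Protocol 1 says of the products: "Clinolipid has approximately one third of the LA content of a 100% SO ILE". Its Table 2 gives the sterol contents.

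The fatty acid profile, phytosterols, cholesterol and squalene are scheduled at baseline, about every 15 days and at end of treatment (Protocol Appendix 1). Protocol 6.7.1 has the investigator review laboratory data, and its Table 5 includes these analytes.

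Under Protocol 6.8.2 and 6.8.5 the unblinded pharmacist judges LA intake against 1–4% of total energy, and "The pharmacist communicates to the patient's nutrition clinician according to the protocol". Section 6.8.2 lets the investigator stay blinded when there are no clinical features, arachidonic acid is normal and LA intake lies in that range.

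**The concern.** The two emulsions differ in the very substances the trial measures in plasma. A plan that foresees no unblinding data gives no one a reason to restrict access to those results. The LA assessment is a second route: it is a function of dose, energy and product, and the clinical team already records dose and energy every day.

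Several steps are matters of judgement and depend on the blind: AE causality, flagging of AEs of special interest, exclusions from the Per Protocol Set, and the size of any LA increase. That last choice can change later Holman Index values. The Holman Index itself is a central laboratory measurement and is not exposed in the same way.

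**Working it through.** **1. Product ratios.** Protocol Table 2, in µg/mL, Intralipid first and Clinolipid second:

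- "Squalene 7.43 ± 0.10 387.45 ± 2.30": 387.45 / 7.43 = 52-fold, higher in Clinolipid.
- "Stigmasterol 65.05 ± 0.52 12.15 ± 0.04": 65.05 / 12.15 = 5.4-fold, higher in Intralipid.
- "Campesterol 55.35 ± 0.48 13.33 ± 0.12": 55.35 / 13.33 = 4.2-fold, higher in Intralipid.
- β-sitosterol: 302.64 / 240.59 = 1.26-fold. Total phytosterols: 439.07 / 274.38 = 1.6-fold.

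Protocol Table 1, % of fatty acids: LA 54.7 / 18.6 = 2.9-fold, higher in Intralipid; oleic acid 59.7 / 20.9 = 2.9-fold, higher in Clinolipid.

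At 3 g/kg/day (15 mL/kg/day of a 0.2 g/mL emulsion), squalene delivered is 15 × 7.43 / 1000 = 0.11 mg/kg/day on Intralipid and 15 × 387.45 / 1000 = 5.8 mg/kg/day on Clinolipid.

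**2. From product to plasma (assumption).** The documents give no plasma levels by arm. Suppose plasma levels are log-normal with log-SD σ between 0.5 and 1.0, and the arms differ by a ratio R. The chance of correctly ranking one patient from each arm is Φ(ln R / (σ√2)):

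| Plasma ratio R | Chance of correct ranking (σ = 1.0 to 0.5) |
|---|---|
| 10 | 0.95–1.00 |
| 5 | 0.87–0.99 |
| 3 | 0.78–0.94 |
| 1.6 | 0.63–0.75 |
| 1.26 | 0.57–0.63 |

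Even a plasma ratio far below 52 would separate patients well on squalene. Sitosterol would separate them little.

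**3. The protocol's own LA example (6.8.5).** LA % of energy = mL/kg/day × g LA/mL × 10 kcal/g ÷ kcal/kg/day × 100. At 8 mL/kg/day and 100 kcal/kg/day:

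- Intralipid: 8 × 0.11 × 10 / 100 = 8.8%.
- Clinolipid: 8 × 0.04 × 10 / 100 = 3.2%.

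Both match the protocol.

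**4. The same formula over Table 4 doses and Table 3 energy targets** (LA per mL from Table 6; 1 g lipid = 5 mL):

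| Group | Day 1, Intralipid | Day 1, Clinolipid | Maintenance, Intralipid | Maintenance, Clinolipid |
|---|---|---|---|---|
| Preterm | 4.6–6.1% | 1.7–2.2% | 11.5–18.3% | 4.2–6.7% |
| Term | 5.5–6.1% | 2.0–2.2% | 13.75–18.3% | 5.0–6.7% |
| Children | 6.9–10.0% | 2.5–3.6% | 13.75–30.0% | 5.0–10.9% |
| Adolescents | 10.0–18.3% | 3.6–6.7% | 10.0–36.7% | 3.6–13.3% |

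The lowest Intralipid value is preterm Day 1: 5 × 0.11 × 10 / 120 = 4.6%. At 9 kcal/g it is 4.1%, still above 4%.

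**5. When the category alone separates the arms.** The dose giving exactly 4% is 0.04 × energy / 5.5 for Intralipid and 0.04 × energy / 2 for Clinolipid. At 120 kcal/kg/day these are 0.87 and 2.4 g/kg/day; at 90 kcal/kg/day, 0.65 and 1.8 g/kg/day. Between the two doses, Clinolipid reads at or below 4% and Intralipid above it. Above the higher dose both read above 4%. Below the lower dose neither exceeds 4%.

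**6. When a number is given.** At the same dose and energy the two candidate percentages differ by 0.11 / 0.04 = 2.75-fold. Intralipid contains 0.2 × 54.7% = 109.4 mg LA/mL. Across the Clinolipid LA range in Protocol 5.1.1 (27.6 to 44.0 mg/mL), the ratio runs from 109.4 / 44.0 = 2.5 to 109.4 / 27.6 = 4.0. Anyone who knows dose and energy can tell which product gave the figure.

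**The case against.** Several limits stand.

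- **Product is not plasma.** A reader might infer that plasma squalene differs 52-fold or that phytosterols as a class reveal the arm. The documents do not show this. The sterol figures come from a single lot. The 4-hour lipid hold before fatty acid samples, unrestricted enteral feeding and pre-randomization lipids all weaken the signal.
- **Release is not stated.** A reader might infer that real squalene and sterol values reach sites, dry runs or the staff who flag AEs of special interest. Neither document says so. Handling details are left to laboratory instructions and a manual that are not among the documents and may restrict release. The planned listings do include these analytes, and neither the SAP nor the protocol sets a masking rule.
- **No percentage is prescribed.** Protocol 6.8.5 says the pharmacist communicates, not that a figure is sent, and ties this to the pathways in 6.8.2 to 6.8.4.
- **The category often does not separate the arms.** At maintenance both usually read above 4%. With 1 g/kg/day advancement, maintenance is reached by about Day 3, and the first scheduled post-baseline sample is Day 15. On Table 6 values the exception at maintenance is the low-dose adolescent (3.6%). On Table 1 percentages the preterm extreme also falls just below 4% (2.5 × 0.186 × 10 / 120 = 3.9%). Otherwise the category is informative mainly at lower doses.
- **Consequences are bounded.** The study is descriptive, with no hypothesis tests, and the primary measurement comes from a laboratory blinded to assignment.

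None of this rescues the sentence, which claims that not even potentially unblinding data are foreseen.

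**Conclusion.** The SAP sentence is wrong as written. Potentially unblinding data are foreseeable from the protocol's own tables: 52-fold for squalene, 5.4-fold for stigmasterol, 4.2-fold for campesterol and about 2.9-fold for LA and oleic acid, against only 1.26-fold for sitosterol and 1.6-fold for total phytosterols. How far plasma values separate the arms is an assumption.

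The LA-intake route is the firmer one. Within Tables 3 and 4 a reading of 1–4% can come only from Clinolipid, yet that is the branch of 6.8.2 in which the investigator may remain blinded. A numeric percentage identifies the arm; a bare reading above 4% does not. This rests on emulsion LA alone, the energy targets in Table 3 and doses of at least 1 g/kg/day.

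The documents do not support a conclusion that the blind has been broken or that the Holman Index is biased. This should be corrected, because judged steps before database lock depend on it.

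**What to change.** **In the SAP.** Replace the sentence in 1.4.4 with a list of potentially unblinding data: the fatty acid profile; squalene, stigmasterol, campesterol and the other sterols reported with them; LA-intake assessments; and pharmacist records. State who may see each before database lock. Withhold them from blinded sponsor and CRO staff, including those who flag AEs of special interest and decide Per Protocol exclusions. Use scrambled or dummy values in blinded dry runs. If the laboratory manual already restricts release, cite it.

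**For sites.** The sponsor should reconcile result release and the LA-adequacy communication in Protocol 6.7.1, 6.8.2, 6.8.3 and 6.8.5 with the blinding in 5.5. Those sections use LA, arachidonic acid and Mead acid results and LA-percentage bands as inputs, so the reconciliation should leave every clinical management rule unchanged. It needs protocol or laboratory-manual wording; the SAP alone cannot do it.

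**Cost.** SAP text, some data-transfer work, and a new duty for an unblinded team. The existing secondary CRO team is described only for DSMB unblinding, so holding these data would have to be assigned. Protocol wording would also need IRB review.
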